6.2.2.5. Duration of response

Duration of Response (DR) is defined, for patients with OR, as the time from the first documentation of objective response (CR or PR) to the date of first documentation of PD or death due to any cause. If a patient has not had an event (PD or death), DR is censored at the date of last adequate tumor assessment. The censoring rules for DR are described in [Table 12](#).

$$\text{DR (months)} = [\text{date of event or censoring} - \text{first date of OR} + 1] / 30.4375$$

Table 12. Outcome and Event Dates for DR Analyses

Scenario	Date of event/censoring	Outcome
PD or death - After at most one missing or inadequate post-baseline tumor assessment, OR - ≤ 16 weeks after the date of randomization	Date of PD or death	Event
PD or death - After 2 or more missing or inadequate post-baseline tumor assessments	Date of last adequate tumor assessment ^a documenting no PD before new anti-cancer therapy is given or missed tumor assessments	Censored
No PD and no death	Date of last adequate tumor assessment ^a documenting no PD before new anti-cancer therapy is given or missed tumor assessments	Censored
Treatment discontinuation due to ‘Disease progression’ without documented progression	Not applicable	Information is ignored. Outcome is derived based on documented progression only.
New anti-cancer therapy given	Date of last adequate tumor assessment ^a documenting no PD before new anti-cancer therapy is given or missed tumor assessments	Censored

^a If there are no adequate post-baseline assessments prior to PD or death, then the time without adequate assessment should be measured from the date of randomization; if the criteria were met the censoring will be on the date of randomization.

Kaplan-Meier estimates (product-limit estimates) will be presented by treatment arm together with a summary of associated statistics including the median DR time with 2-sided 95% CIs. In particular, the DR rates at 3, 6 and 12 months will be estimated with corresponding 2-sided 95% CIs. The CIs for the median will be calculated according to Brookmeyer and Crowley (1982) and the CIs for the survival function estimates at the time points defined above will be derived using the log-log transformation according to Kalbfleisch and Prentice (2002) (conftype=loglog default option in SAS Proc LIFETEST) with back transformation to a CI on the untransformed scale. The estimate of the standard error will be computed using Greenwood’s formula.

DR will be displayed graphically and analyzed using Kaplan-Meier methodology. If the number of patients with OR is small, the Kaplan-Meier method may not provide reliable estimates. In this case, only descriptive statistics or listings will be provided.

Frequency (number and percentage) of patients with each event type (PD or death) and censoring reasons will be presented by treatment arm. Reasons for censoring will be summarized according to the categories in Table 13 following the hierarchy shown.

Table 13. DR Censoring Reasons and Hierarchy

Hierarchy	Condition	Censoring Reason
1	Start of new anti-cancer therapy	Start of new anti-cancer therapy
2	Event after 2 or more missing or inadequate post-baseline tumor assessments/date of randomization	Event after 2 or more missing assessments ^a
3	No event and [withdrawal of consent date \geq date of randomization OR End of study (EOS) = Patient refused further follow-up]	Withdrawal of consent
4	No event and lost to follow-up in any disposition page	Lost to follow-up
5	No event and [EOS present OR disposition page for any epoch after screening says patient will not continue into any subsequent phase of the study] and no adequate post-baseline tumor assessment	No adequate post-baseline tumor assessment
6	No event and none of the conditions in the prior hierarchy are met	Ongoing without an event

^a 2 or more missing or inadequate post-baseline tumor assessments.

6.2.2.6. Time to response

Time to response (TTR) is defined, for patients with OR, as the time from the date of randomization to the first documentation of objective response (CR or PR) which is subsequently confirmed.

$$\text{TTR (in months)} = [\text{first date of OR} - \text{date of randomization} + 1]/30.4375$$

TTR will be summarized using simple descriptive statistics (mean, SD, median, min, max, Q1, Q3).

6.2.3. Pharmacokinetic endpoints

The following pharmacokinetic analyses will be based on the PK analyses set.

C_{trough} and C_{max} for avelumab will be summarized descriptively (n, mean, SD, CV, median, minimum, maximum, geometric mean, its associated CV, and 95% CI) by co-primary population, cycle, and day. Pharmacokinetic parameters for avelumab will be taken from observed plasma concentration-time data as described in [Section 3.2.4](#).

C_{trough} will be summarized for all pre-dose samples collected prior to avelumab dosing on the same visit day. C_{max} will be summarized for all post-dose samples collected +/- 10% or +/- 30 minutes from the end of infusion, whichever is further from the end of infusion time.

Presentation of pharmacokinetic data will include:

- Descriptive statistics (n, mean, SD, %CV, median, minimum, maximum) of plasma concentrations will be presented in tabular, cycle, day and nominal time.

- Linear-linear plots of mean and median plasma concentrations by nominal time for avelumab will be presented for PK sampling days by cycle, and study day.
- Pharmacokinetic parameters for avelumab will be listed and summarized by cycle and study day using descriptive statistics (n, mean, SD, %CV, median, minimum, maximum, geometric mean and its associated %CV, and 95% CI). Box plots for C_{max} and C_{trough} for avelumab will be generated. Individual data points, the geometric mean and the median of the parameter will be overlaid on the box plots. If Arm A has limited evaluable PK data ($n < 4$), matchstick plots showing changes C_{max} and C_{trough} in individual patients will then be generated. The geometric mean of the parameter will be overlaid in the plots.

6.2.4. Population pharmacokinetic endpoints

Pharmacokinetic and pharmacodynamic data from this study may be analyzed using modeling approaches and may also be pooled with data from other studies to investigate any association between avelumab exposure and biomarkers or significant safety/efficacy endpoints. The results of these analyses, if performed, may be reported separately.

6.2.5. Biomarker endpoints

Secondary endpoints in the study are candidate predictive biomarkers in tumor tissue including, but not limited to, PD-L1 expression and tumor infiltrating CD8+ T lymphocytes.

Exploratory endpoints in the study include peripheral blood and additional tumor tissue biomarkers consisting the levels of cells, deoxyribonucleic acid (DNA), ribonucleic acid (RNA), or proteins that may be related to anti-tumor immune response and/or response to or disease progression on avelumab, such as genes related to IFN- γ or transforming growth factor (TGF)- β .

Biomarker data will be analyzed based on the biomarker analysis sets as defined in [Section 4.3.3](#).

Biomarkers will be summarized at all timepoints described below:

- Blood biospecimens for exploratory assessments: C1D1, C1D15 (Arm A only), C2D1, C3D1, C5D1 and EOT.
- Tumor based biomarkers, archival FFPE Tumor Tissue Block: screening
- Tumor based biomarkers, de novo Tumor Biopsy: screening and End of Treatment.

Descriptive summary statistics (mean, SD, median, Q1, Q3, coefficient of variation, minimum, and maximum), at each timepoint and ratio to baseline at each visit (if appropriate) will be provided for avelumab for continuous variables. Non-continuous variables will be summarized using n/N and percent at each timepoint and treatment arm.

For each biomarker or set of biomarkers, patients may be classified as positive, negative, or some other category according to scoring algorithms and cut-offs established from external

sources. If no external standards exist, biomarkers may be stratified using the median: \leq median and $>$ median. Percent of patients in each category will be tabulated and tested using methods for categorical variables.

Biomarkers may be included as a covariate in a survival analysis model; biomarkers will be stratified on the above-mentioned classifications. Using a Cox proportional hazard model, HR, 95% CI, and p-values will be calculated for OS (primary endpoint) and PFS by BICR assessment (secondary endpoint). Further analyses may include the biomarker status by treatment arm interaction. If there are fewer than 20 events in a subgroup, or the HR is not estimable, only descriptive summary statistics will be provided.

Biomarker value or classification will also be provided for percent responders. For analyses using the actual value, the value will be summarized by response category (yes or no to being a responder, defined as CR or PR from best overall response). The Wilcoxon Rank-Sum test will be used as discussed above. For analyses using the biomarker classification, a contingency table will be produced, and the treatment arms compared using a Fisher's exact test. If there are less than 5 observations in a cell, no p-value will be produced for either the Fisher's exact test.

For all biomarker analytes, it is not possible to pre-specify all possible analyses of interest. Thus, the biomarker results will follow the 2-Step Methodology approach. The analyses of initial interest will be performed as described above. A second set of analyses will be defined and performed based on the results from the first set of analyses. It is anticipated that if there are, for example, 100 analyses run in the first step, no more than 20 analyses will be run in the second step; estimates will get larger or smaller depending on the number of analyses run in the first step.

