9.4.1. Statistical Analysis of Biomarker Endpoints

It is possible that, during the course of this study, emerging data and/or methods will suggest additional patient selection strategies beyond the verified GMP PD-L1 test used to define the co-primary populations. Retrospective analysis of biomarkers such as PD-L1 (using a different method from the GMP test) and CD8 are planned as a secondary objective to enable refinements in patient selection strategy, whether via technical modifications or revised thresholds. These methods may be single- or multi-analyte based on IHC or immunofluorescence. Further exploratory analyses may also be performed to assess the predictive and/or pharmacodynamic utility of additional methods, such as profiling of gene expression signatures indicative of immune activation. The Biomarker Analysis Set will be used for the analysis of biomarker endpoints.

Biomarkers will be assessed separately for whole blood, serum, plasma, archival tumor tissue, and de novo tumor biopsies. In each case, summaries of baseline levels, changes from baseline (where appropriate), gene alteration or biomarker signature status, will be reported. For continuous variables summary statistics may include the mean, ratio to baseline, standard deviation, median, 25th and 75th quartile, %CV and minimum/maximum levels of biomarker measures; for categorical variables, the summary may include number, percentage, and odds ratio, as appropriate.

Data from biomarker assays will be analyzed using graphical methods and descriptive statistics such as linear regression, t-test, and analysis of variance (ANOVA). The statistical approach may examine correlations of biomarker results with pharmacokinetic parameters and measures of anti-tumor efficacy.

Regarding exploratory biomarkers, the data analysis will be conducted with the goal of identifying predictive and/or pharmacodynamic (ie, baseline and change from baseline values) biomarkers associated with clinical outcome, encompassing both safety and efficacy. Candidate biomarkers will be validated in subsequent trials.

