3.2.6. Biomarker endpoints

- Tumor tissue biomarkers including, but not limited to, PD-L1 expression and tumor-infiltrating CD8+ T lymphocytes.

Table 3. Biomarker Definition and Determination

Parameter	Definition	Method of Determination
PD-L1 expression	The number of PD-L1-positive cells and/or qualitative assessment of PD-L1 staining on tumor and inflammatory cells in regions of interest that are defined by tumor cell morphology and the presence or absence of inflammatory cells	Pathologist, assisted by image analysis
Tumor infiltrating CD8+ lymphocytes	The number of CD8+ cells per unit area and the percent of counted cells that are scored as CD8+	Pathologist, assisted by image analysis

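### Where no external cut-off exists, SAP 6.2.5 provides only a median split for biomarkers in the OS and PFS Cox models; a continuous term should be added

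*SAP*

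**What the plan says.** Evaluating candidate predictive biomarkers in pre-treatment tumor tissue is a secondary objective (Protocol 2.1, SAP 2.1). SAP Table 3 (section 3.2.6) defines the CD8 marker as "The number of CD8+ cells per unit area and the percent of counted cells that are scored as CD8" positive, which is a continuous scale.

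SAP 6.2.5 then sets out the analysis:

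- Patients may be classified by externally established algorithms and cut-offs. Failing that, "If no external standards exist, biomarkers may be stratified using the median", giving two groups.
- For time-to-event endpoints, "Biomarkers may be included as a covariate in a survival analysis model", and in that case "biomarkers will be stratified on the above-mentioned classifications".
- From the Cox model, "HR, 95% CI, and p-values will be calculated for OS" and for PFS by BICR.
- "Further analyses may include the biomarker status by treatment arm interaction".
- For tumor response, the same section separates analyses of the actual value from analyses of the classification. It makes no such separation for OS or PFS.

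Protocol 9.4.1 says the retrospective work on markers such as CD8 and PD-L1 by another method is meant "to enable refinements in patient selection strategy, whether via technical modifications or revised thresholds".

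**The concern.** A marker counted on a continuous scale is reduced to high or low before it meets the endpoints that matter most. The SAP recognises the measured value, since it uses it for response, but describes no use of it in the survival models. Cutting a continuous predictor at its median usually discards information. Tests of treatment-by-marker interaction have little to spare, so a real predictive marker becomes easier to miss.

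Two features of the plan add to this. The two-step approach in SAP 6.2.5 chooses the second set of analyses from the results of the first, at roughly 20 for every 100, so a marker missed at step one may not be taken further. And the sample median belongs to this sample: a high-versus-low hazard ratio says little about where a selection threshold should lie, or how the effect changes along the marker scale.

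**Working it through.** **Inputs from the documents.** 668 patients randomized 1:1; 425 OS events in all patients (HR 0.7, one-sided 0.015, 93% power); 219 in PD-L1-positive patients (HR 0.65, one-sided 0.01, 80% power); control median OS 12 months; 28-month accrual (SAP 5.1.1).

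**Inputs that have to be assumed.** For the interaction test the documents give no alpha, effect size, power or marker distribution. I take two-sided 0.05, to match the 95% CI, and show ranges for the rest.

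**Step 1: the plan's own figures.** Fixed-sample power is Φ(√(D/4)·|ln HR| − z).

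- All patients: √(425/4) × 0.3567 = 3.68; 3.68 − 2.17 = 1.51; power 93.4%. With the two-look Lan-DeMets O'Brien-Fleming design, 93.1%.
- PD-L1-positive: √(219/4) × 0.4308 = 3.19; 3.19 − 2.33 = 0.86; power 80.5%. With two looks, 80.2%.
- The interim efficacy boundaries come out at 2.595 and 2.947, as in SAP Table 5.

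The primary design reproduces and is not in question.

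**Step 2: information kept by a median split.** For an effect linear in X, the relative efficiency is the squared correlation between X and the indicator that X exceeds its median. For a standard normal X, the covariance is 1/√(2π) = 0.399 and the SD of the indicator is 0.5. The correlation is therefore 0.798 and its square 2/π = 0.637. About 36% of the information is lost; 425 deaths then count as about 425 × 0.637 = 271.

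**Step 3: power of the interaction test.** With 1:1 allocation and a marker in SD units, the standard error of the interaction is 2/√D. At D = 425, 80% power on the continuous scale needs a noncentrality of 1.960 + 0.842 = 2.802. That is a ratio of hazard ratios of exp(−2.802 × 2/√425) = 0.76 per SD. After the split the noncentrality is 2.802 × 0.798 = 2.236, and power is Φ(2.236 − 1.960) = about 61%.

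| Continuous | After split | Loss (points) |
|---|---|---|
| 50% | 34.6% | 15.4 |
| 70% | 50.9% | 19.1 |
| 80% | 60.8% | 19.2 |
| 90% | 73.5% | 16.5 |
| 95% | 82.0% | 13.0 |

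Starting from 80%, the loss is 16.7 points at two-sided 0.10 and 15.2 at 0.15.

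**Step 4: simulation.** Cox models with treatment, marker and interaction were fitted to 668 patients at 425 events (2,000 runs, exponential survival, uniform accrual over 28 months, normal marker, ratio 0.76 per SD). Power was 80.4% continuous and 59.4% split. With no interaction (1,000 runs) the rejection rates were 4.2% and 4.4%, so the level is held.

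**Step 5: sensitivity to the assumptions.** With the effect linear on the scale shown and 80% starting power:

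| Marker distribution | Information lost | Power after split |
|---|---|---|
| Two-component normal mixture | 17% | 72.3% |
| Uniform | 25% | 67.9% |
| Normal | 36% | 60.8% |
| t, 5 df | 46% | 53.9% |
| Exponential | 52% | 49.2% |
| Lognormal, σ = 1 | 73% | 31.0% |

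If instead the true effect is a step at the median, the order reverses: in simulation the split has 77.8% power and the continuous term 60.8%.

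**The case against.** The strongest reply is that the SAP commits to very little here. The median split, the survival model and the interaction are each worded as *may*, and no alpha is allocated to any of them. SAP 6.2.5 concedes that not every analysis of interest can be specified in advance, and its second step could include a continuous or spline model. Protocol 9.4.1 mentions linear regression and correlation of biomarker results with efficacy measures. The documents give no more reason to expect log-linearity than to expect a step. Protocol 9.2.6 also limits the Biomarker Analysis Set to treated Arm A patients, among whom no treatment interaction can be fitted.

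Much of this stands. It rules out treating the power loss as a fact of this trial, and it keeps the point within secondary and exploratory work. It does not supply the missing term. Once a survival model is fitted, use of the classes is worded as *will*. The protocol's regression and correlation language specifies no continuous Cox model, and Protocol 9 leaves detailed methodology to the SAP. Because the true shape is unknown, a continuous term with a shape check is the safer main analysis, with the split alongside it. The Arm A restriction conflicts with SAP 4.3.3, which does not limit the set by arm, so it is something to resolve. If the set stays Arm A only, the same efficiency argument applies to the marker's own effect in a within-arm model.

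A reader might also infer that the sample median is to become the revised selection threshold. Neither document says so, and Protocol 9.4.1 leaves validation of exploratory candidates to later trials.

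**Conclusion.** The point holds as a gap in the described method: for continuous markers without an external cut-off, the OS and PFS Cox models have a median split as the only stated route. Its cost is conditional. With a roughly normal marker, a log-linear effect and two-sided 0.05, the split keeps about 64% of the information. An 80% test becomes one of about 61%, and the loss is 13 to 19 points for starting powers of 50% to 95%. The 425-event illustration also assumes a marker value for every patient behind those deaths and both arms in the analysis.

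A reader might infer that the plan will in fact split every such marker and so lose 36% of the information and about 20 points of power. The documents do not support that: the steps are optional, the necessary assumptions are not stated, other distributions give losses from 17% to 73%, and a step at the median favors the split. The primary OS test is untouched. So is the PD-L1 co-primary population, whose scoring algorithm is to be fixed before sample analysis (SAP 4.1). This is a worthwhile, inexpensive improvement to a secondary objective and does not threaten the trial's main conclusions.

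**What to change.** In SAP 6.2.5, for continuous markers with no externally established cut-off:

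- Fit the OS and BICR-PFS Cox models on the continuous value, log-transformed if skewed, and report the hazard ratio per SD.
- Add a treatment-by-marker term where both arms are included.
- Fit a restricted cubic spline with 3 knots as a check on shape, which would also help reveal a threshold-like effect.
- Keep the median split for tables and Kaplan-Meier display, and leave externally defined cut-offs as planned.

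Reconcile Protocol 9.2.6 (treated Arm A patients only) with SAP 4.3.3 (not limited by arm), so that it is clear whether and in whom the interaction can be fitted.

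The cost is SAP wording and one extra model per marker, plus the spline check, on data already collected. The small downside is that a per-SD hazard ratio is harder to explain than high versus low, which is why the split display stays.

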The current “watch-and-wait” approach for the management of metastatic UC following response to first-line chemotherapy prior to initiation of second-line treatment has not proven to be effective because almost all patients eventually relapse. A multicenter Phase 2 study of sunitinib as maintenance therapy in patients with advanced UC was recently reported.³² Although the study terminated prematurely due to low patient recruitment, it provided a different perspective on the treatment of this disease (ie, maintenance therapy following response to first-line chemotherapy in an attempt to improve the durability of the initial response). Very recently, Powles et al reported the results of a Phase 2/3 study of lapatinib as maintenance treatment after first-line chemotherapy in patients with HER1/HER2-positive UC.³³ Between 2007 and 2013, 455 patients were screened and 232 HER 1 or 2 positive patients randomized to lapatinib (n = 116) or placebo (n = 116). The median PFS, median OS, and objective response rate (ORR) for lapatinib vs. placebo were 4.6 months (95% CI: 2.8 – 5.4) vs. 5.3 months (95% CI: 3.0 – 5.9) (HR: 1.04 [95% CI: 0.79 – 1.39] p = 0.77); 12.6 months (95% CI: 9.5 – 16.2) vs. 11.9 months (95% CI: 10.6 – 15.8) (HR 0.98 [95% CI: 0.71 – 1.35] p = 0.89); and 13.8% vs. 7.8%, respectively (p = 0.14). Subset analysis of 1) HER1/HER2 3+ positive UC patients on immunohistochemistry (IHC), 2) HER1-positive UC patients, and 3) HER2-positive UC patients showed no significant benefit for lapatinib compared to placebo in median PFS (HR 0.94, 0.99, and 1.19 respectively; p >0.05 for each) or median OS (HR: 0.76, 0.92, and 1.03 respectively; p >0.05 each). In addition, a study evaluating vinflunine^{34,35} as a maintenance UC treatment is currently ongoing.

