In the ongoing Phase 1 study EMR 100070-001, 53 patients were treated with avelumab doses of 1.0, 3.0, 10.0, and 20.0 mg/kg administered IV Q2W in the dose escalation phase. The 10 mg/kg dose level was selected for further study and a summary of pooled safety data from 1738 patients treated at this dose level in studies EMR 100070-001 and EMR 100070-003 (N=1738) is available with a data cutoff date of 09 June 2016.¹⁹ The most frequently reported (incidence >5%) treatment-related adverse events were fatigue (17.7%), infusion-related reaction (17.0%), nausea (8.6%), diarrhea (7.1%), chills (6.7%), pyrexia (6.1%), decreased appetite (5.2%), and hypothyroidism (5.0%).

Updated data from a pooled analysis of 249 patients enrolled in two advanced UC expansion cohorts in study EMR 100070-001 was recently published.⁷⁵ Patients were included regardless of PD-L1 expression levels. The median age was 68 years and 124 (50%) patients received 2 or more prior treatments for advanced or metastatic disease. At the time of the analysis (09 June 2016 data cut-off), the median followup was 9.9 months (range 4.3-12.1 months) and 60 (24%) patients were still on treatment. Among 161 post-platinum patients with at least 6 months of follow-up, the ORR was 17% (95% CI: 11-24%), including 9 CRs and 18 PRs. The disease control rate (DCR) was 40%, including 37 patients who had SD as their best response. An analysis using a cut-off of $\geq 5\%$ for the expression of PD-L1 on tumor cells in 139 evaluable patients showed a 24% (15/63) ORR in the PD-L1 positive population and 13% (10/76) in the PD-L1 negative population, supporting that avelumab has anti-tumor activity in both the PD-L1 positive and negative populations. The median PFS was 11.9 weeks (95% CI: 6.1-18.0 weeks) and 6.1 weeks (95% CI: 5.9-8.0 weeks) in the PD-L1 positive and negative populations, respectively. The median OS was 8.2 months (95% CI: 5.7-13.7 months) and 6.2 months (95% CI: 4.3-14.0 months) in patients with PD-L1 positive and negative tumors, respectively.

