5. GENERAL METHODOLOGY AND CONVENTIONS

5.1. Hypotheses and Decision Rules

5.1.1. Hypotheses and sample size determination

The study is designed to test, in parallel, the following hypotheses:

$$H_{0 \text{ All patients}}: HR_{OS (Arm A/Arm B)} \geq 1, \text{ versus } H_{a \text{ All patients}}: HR_{OS (Arm A/Arm B)} < 1$$

$$H_{0 \text{ PD-L1+}}: HR_{OS (Arm A/Arm B)} \geq 1, \text{ versus } H_{a \text{ PD-L1+}}: HR_{OS (Arm A/Arm B)} < 1$$

where HR_{OS} represents the hazard ratio for OS in the experimental arm vs the control arm.

Approximately 668 patients will be randomized to the treatment arms using a 1:1 randomization, stratified by best response to chemotherapy (CR or PR vs. SD) and site of metastasis (visceral vs. non-visceral) at time of initiating first-line chemotherapy. The type 1 error rate will be split between the co-primary populations to preserve the overall type 1 error rate for the study at 0.025 one-sided. It is estimated that at least 50% of the randomized patients will have adequate tissue for analysis and be determined to have PD-L1-positive tumors.

The sample size for this study is determined based on the following assumptions:

- For all patients and patients with PD-L1-positive tumors receiving BSC alone after first-line chemotherapy, the median OS is 12 months (Powles et al, 2015).
- For all patients receiving avelumab + BSC after first-line chemotherapy, the median OS is assumed to be 17.1 months.

- For patients with PD-L1-positive tumors receiving avelumab + BSC after first-line chemotherapy, the median OS is assumed to be 18.5 months.

This corresponds to a hazard ratio (HR) of 0.7 for all patients and 0.65 for patients with PD-L1-positive tumors under the exponential model assumption.

For all patients, if the true HR is 0.7 under the alternative hypothesis, a total of 425 OS events will be required to have 93% power to detect a HR of 0.7 using a one-sided log rank test at a significance level of 0.015 and a 2-look group-sequential design with Lan-DeMets (O'Brien-Fleming) α -spending function to determine the efficacy boundary and a Gamma Family (-8) β -spending function to determine the non-binding futility boundary.

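### SAP 6.2.5 withholds the Fisher exact p-value whenever a cell is below 5, although the test needs no minimum cell count and is most useful in sparse tables

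*SAP*

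**What the plan says.** SAP 6.2.5 (Biomarker endpoints) sets out how biomarkers are related to response. The outcome is binary: "yes or no to being a responder, defined as CR or PR from best overall response". For biomarkers used as a classification, "a contingency table will be produced, and the treatment arms compared using a" Fisher's exact test. The next sentence is the rule at issue: "If there are less than 5 observations in a cell, no p-value will be produced". It goes on to name only Fisher's test, but after the word *either*, so a second test name appears to have been lost.

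No reason is given for the threshold. Nothing replaces the withheld p-value, and no other section lifts the rule.

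The same section says that, where no external cut-off exists, "biomarkers may be stratified using the median". It also says that "it is not possible to pre-specify all possible analyses of interest", so a second set of analyses will be defined from the results of the first.

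**The concern.** The rule of 5 is a convention for tests that rely on a chi-square approximation, where small (expected) counts make the approximation poor. Fisher's test conditions on the table margins and uses the exact null distribution, so no approximation needs protecting. The SAP therefore picks the small-sample test and then switches it off in small samples.

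The rule is also not neutral about which results it removes. It acts on the smallest cell, and a cell is often small because one arm has almost no responders. Those tables can show the largest contrasts. Because the second step is chosen from first-step results, a withheld p-value could also influence what is examined next.

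**Working it through.** The plan states no figure for this rule, so there is nothing to reproduce. Three checks follow. Each takes the table to be responder yes/no by treatment arm within a biomarker category.

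**Inputs**
- Randomisation: "Approximately 668 patients will be randomized to the treatment arms using a 1:1 randomization" (SAP 5.1.1), so 668/2 = 334 per arm. A median split with everyone evaluable gives 334/2 = 167 per arm in each half.
- Response rates for illustration: 13.8% (lapatinib) and 7.8% (placebo) from the maintenance trial described in Protocol 1.2.3.1. For avelumab in a pretreated cohort, Protocol 1.2.3.2 "showed a 24% (15/63) ORR in the PD-L1 positive population".
- Assumed, because the documents give no values: group sizes below 167, a 3% response rate as a low case, and two-sided 0.05 for these tests. One route to n = 83 is a median split within the PD-L1-positive population: 334 patients give 167 per arm, and 167/2 is about 83. SAP 6.2.5 does not say the tables will be cut this way.

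**1. Is the test valid in sparse tables?** All pairs of binomial outcomes were enumerated for two equal arms with the same true rate, and the probabilities of tables with Fisher p ≤ 0.05 were summed. At 7.8% in both arms the actual type I error is:

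| n per arm | Type I error |
|---|---|
| 30 | 0.006 |
| 60 | 0.018 |
| 84 | 0.025 |
| 167 | 0.030 |

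Over a grid of common rates from 2% to 50%, the largest value was 0.013 (n = 10), 0.025 (n = 20) and 0.027 (n = 30). Removing the rule does not inflate error; the test is conservative here.

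**2. How often would the rule fire?** For one group, P(X ≤ 4) = Σ C(n,k) pᵏ(1−p)ⁿ⁻ᵏ, summed over k = 0 to 4. For n = 40 and p = 0.078 the terms are 0.039 + 0.131 + 0.217 + 0.232 + 0.182 = 0.801.

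| n in group | p = 7.8% | p = 3% (assumed) |
|---|---|---|
| 40 | 80% | 99% |
| 64 | 43% | 96% |
| 83 | 22% | 90% |
| 116 | 5% | 73% |
| 167 | 0.3% | 44% |

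Counting all four cells, with true rates of 13.8% and 7.8%, some cell is below 5 with probability 97% (n = 30 per arm), 53% (60), 21% (84), 5% (116) and 0.3% (167).

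**3. What is hidden?** With true rates of 24% and 7.8%:

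| n per arm | P(Fisher p ≤ 0.05) | Part of it in suppressed tables |
|---|---|---|
| 30 | 0.263 | 0.262 |
| 60 | 0.61 | 0.41 |
| 84 | 0.78 | 0.20 |
| 167 | 0.98 | 0.003 |

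Individual tables that would carry no p-value include 12/60 vs 2/60 (p = 0.008), 10/50 vs 0/50 (p = 0.001) and 20/84 vs 3/84 (p = 0.0002). The second can be checked by hand: 2 × C(50,10)/C(100,10) = 2 × 0.000593 = 0.0012.

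**The case against.** The best defence is that this is a low-information convention, not a misplaced chi-square condition. SAP 6.2.5 also falls back to descriptive statistics when a subgroup has fewer than 20 events in the Cox analyses. SAP 6.2.2.5 allows the same for duration of response when responders are few. In a screen where the SAP itself gives 100 first-step analyses as an example, not printing p-values from sparse tables is a defensible preference.

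Part of this stands. The SAP gives no rationale, so a chi-square origin is an inference, and sparse tables are imprecise. But the Cox model is a large-sample method, and its threshold does not carry over to an exact test. Imprecision is better shown by the cell counts or an interval than by silence.

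Two stronger readings are tempting, and the documents support neither.
- A reader might infer that the rule removes the test in the only place where it is valid. Fisher's test is valid at every cell count; small cells are where it is most needed.
- A reader might infer that the secondary objective on predictive biomarkers goes largely untested. Only the Fisher p-value is withheld. The contingency table is still produced, as are the Wilcoxon test on actual values and the Cox models for OS and PFS, with a possible biomarker-by-arm interaction and subject to the 20-event rule. For PD-L1 status, SAP 6.4 also plans a response odds ratio with its 95% CI. The Fisher comparison is between arms and is not itself a test of predictive interaction.

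**Conclusion.** The point holds as a minor one. As written, the rule withholds valid p-values and does so selectively, and the sentence is incomplete in any case.

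The size is uncertain because it rests on assumed group sizes and response rates. At a full median split and 7.8% response the rule would hardly ever fire. In smaller groups, or with response near 3%, it would fire often. The 7.8% comes from a placebo arm of HER1/HER2-selected patients and the 24% from pretreated patients, so neither predicts this trial.

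The primary OS tests, PFS and the main response analysis (Cochran-Mantel-Haenszel with Clopper-Pearson intervals, SAP 6.2.2.3) are untouched. No alpha is allocated to the biomarker tests.

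**What to change.** Delete the suppression sentence for Fisher's test. If an asymptotic test was meant to stand beside it, name that test and restrict the rule to it. Report the Fisher p-value together with the cell counts whatever the cell size.

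For 2×2 tables an exact confidence interval for the odds ratio may be added, with a note that it is unbounded on one side when a cell is zero. It should not be promised for every table: SAP 6.2.5 allows more than two biomarker categories, and a larger table has no single odds ratio.

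The cost is slightly more output, including some imprecise results from sparse tables. No data collection, sample size or error allocation changes.
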